8.2.5 Dermatology Life Quality Index (DLQI)

The DLQI, is a dermatology-specific Quality of Life (QoL) instrument. Age appropriate- DLQI will be completed at the time points designated in the SoA ([Table 1](#)). The standard DLQI is a questionnaire designed for subjects aged ≥ 16 years that measures the impact of skin disease on the previous week’s QoL. There are 10 questions related to the following topics: symptoms (from drug effect or irritant/allergic contact dermatitis), embarrassment, shopping and home care, clothes, social and leisure, sport, work or study, close relationships, sex, treatment (see [Appendix 8](#)). Questions are scored from 0 to 30 with a possible score range from 0 (no impact of skin disease on QoL) to 30 (maximum impact on QoL). The score ranges are shown in Table 11.

Table 11 Dermatology Life Quality Index Scale

Score	Description
0 to 1	No effect on patient’s life
2 to 5	Small effect
6 to 10	Moderate effect
11 to 20	Very large effect
21 to 30	Extremely large effect.

The minimal clinically important difference is the minimum difference in score that is meaningful for a subject. This is considered 4 points for inflammatory skin diseases.

Children’s DLQI will be used for subjects < 16 years of age to measure the impact of skin disease on the previous week’s QoL. There are 10 questions related to the following topics: symptoms (from drug effect or irritant/allergic contact dermatitis) and feelings, leisure, school or holidays, personal relationships, sleep, treatment (see [Appendix 9](#)). Questions are scored from 0 to 30 with a possible score range from 0 (no effect on child’s life) to 30 (extremely large effect). The score ranges are shown in Table 12.

Table 12 Children's Dermatology Life Quality Index Scale

Score	Description
0 to 1	No effect on child's life
2 to 6	Small effect
7 to 12	Moderate effect
13 to 18	Very large effect
19 to 30	Extremely large effect.

8.2.6 Ichthyosis Quality of Life (IQoL-32)

The IQoL-32 is a short and easy-to-use questionnaire containing 32 questions and organized in 7 domains (see [Appendix 10](#)). The questions are specifically dedicated to ichthyosis and explore all disease particularities such as skin pain/discomfort (from drug effect or irritant/allergic contact dermatitis), ear- and eye-related problems, heat intolerance, skin odor, scalp involvement, restrictions related to the disease (dressings, sports, leisure), expenses, psychological aspects, and consequences of the treatment: time for skin care, oily skin or clothes, and side effects. The IQoL-32 is designed for subjects >15 years of age.

8.2.7 Photography

Photographs of all four VIIS Assessment Areas (upper arms, lower legs, upper back, dorsal foot) will be taken at the time points designated in the SoA ([Table 1](#)) at preselected sites per Photographic Guide provided by the Sponsor.

8.3 Safety Assessments

8.3.1 Physical Examination

A physical examination will be performed at the time points designated in the SoA ([Table 1](#) and Table 13), including head and neck, dermatological, cardiovascular, respiratory, gastrointestinal (abdomen), and gross motor and gait body assessments.

Abnormalities at Visit 1 (Screening) and Visit 2 (Baseline) prior to treatment will be recorded as medical history. Any new or worsening abnormalities at Visit 6 and/or Visit 9 (EOS) in the study or at Visit 8 (EOS) in the Optional Maximal Use arm will be recorded as AEs.

If there are less than two weeks between Visit 1 (Screening) and Visit 2 (Baseline), the physical examination at the Visit 2 (Baseline) includes only a dermatological assessment.

8.3.2 Vital Signs

Vital signs including temperature, systolic and diastolic blood pressure, heart rate, and respiration rate will be measured at the time points designated in the SoA ([Table 1](#) and Table 13). Assessments will be made after the subject has rested in a seated position for at least 5 minutes in a quiet setting without distractions (e.g., television, cell phones). Height and weight will only be measured at Visit 1 (Screening).

8.3.3 Local Skin Reactions and Evaluation of Allergic Contact Dermatitis

At the time points designated in the SoA ([Table 1](#) and Table 13), the Investigator or designee will evaluate LSRs known to be associated with retinoids (burning/stinging, erythema, erosions, and edema) or other causes regardless of blinded causality assessment within the areas treated with study medication using a 4-point ordinal scale where 0 = none, 1 = mild, 2 = moderate, and 3 = severe.

Note: At Visit 2 (Baseline), the LSR assessment must be performed prior to the application of the study medication.

For drug interruption due to LSRs, refer to structured drug interruption scheme (drug reduction) described in [Section 7.1](#).

Allergic contact dermatitis is defined as a dermatitis that lasts at least 2 weeks, does not begin immediately after drug application (for example, reaction begins after first 24 hours of drug application) and becomes eczematous over time.

If at any point during treatment the Investigator believes that the subject is experiencing an allergic contact dermatitis, the subject should undergo investigator directed patch testing, as defined in [Appendix 11](#).

8.3.4 Clinical Safety Laboratory Assessments

Urine and blood samples will be collected from each subject for safety laboratory analyses at the time points designated in the SoA ([Table 1](#) and Table 13).

Subjects must be fasting (at least 8 hours) for Visit 1 (Screening) and, if possible, for Visit 6 and the EOS visit; however, if a subject arrives at the clinic for the EOS visit without fasting for at least 8 hours, laboratory specimens may be collected as non-fasting, at the discretion of the Investigator, and with the appropriate fasting status documented on the laboratory requisition form.

See [Appendix 2](#) for the list of clinical laboratory tests to be performed.

8.3.5 Pregnancy Testing

Serum hCG pregnancy tests and UPT will be performed at the time points designated in the SoA ([Table 1](#) and Table 13) for WOCBP. Women who are pregnant or breastfeeding may not be administered TMB-001 ointment.

Detailed information on pregnancy reporting is presented in [Appendix 4](#).

8.4 Adverse Events

All AEs will be recorded. At each post-baseline visit, subjects will also be questioned specifically about the status of any ongoing AEs.

The definitions of an AE or SAE can be found in [Appendix 3](#).

AEs will be reported by the subject (or, when appropriate, by a caregiver, surrogate, or the subject's legally authorized representative).

Care will be taken not to introduce bias when detecting AEs and/or SAEs. Open-ended and non-leading verbal questioning of the subject is the preferred method to inquire about AE occurrences.

The Investigator and any designees are responsible for detecting, documenting, and recording events that meet the definition of an AE or SAE and remain responsible for following up AEs that are serious, considered related to the study medication or study procedures, or that caused the subject to discontinue the study. The trial blind may be broken for an individual only if knowledge of the investigational medicinal product is essential for clinical management of the subject.

8.4.1 Time Period and Frequency for Collecting Adverse Event and Serious Adverse Event Information

All AEs and SAEs will be collected from signing the ICF until the EOS visit at the time points specified in the SoA ([Table 1](#) and Table 13).

All SAEs will be recorded and reported to the Sponsor or designee within 24 hours, as indicated in [Appendix 3](#). The Investigator will submit any updated SAE data to the Sponsor within 24 hours of it being available.

After the initial AE/SAE report, the Investigator is required to proactively follow each subject at subsequent visits/contacts. All SAEs will be followed until resolution, stabilization, the event is

otherwise explained, or the subject is lost to follow-up (as defined in [Section 7.3](#)). Further information on follow-up procedures is given in [Appendix 3](#).

Investigators are not obligated to actively seek AE or SAE information after the conclusion of study participation. However, if the Investigator learns of any SAE, including a death, at any time after a subject has been discharged from the study, and he/she considers the event to be reasonably related to the study medication or study participation, the Investigator must promptly notify the Sponsor.

The methods of recording, evaluating, and assessing the causality of AEs and SAEs and the procedures for completing and transmitting SAE reports are provided in [Appendix 3](#).

8.4.2 Regulatory Reporting Requirements for Serious Adverse Events

Prompt notification by the Investigator to the Sponsor of an SAE is essential so that legal obligations and ethical responsibilities towards the safety of subjects and the safety of a study treatment under clinical investigation are met.

The Sponsor has a legal responsibility to notify both the local regulatory authority and other regulatory agencies about the safety of a study treatment under clinical investigation. The Sponsor will comply with country-specific regulatory requirements relating to safety reporting to the regulatory authority, Institutional Review Boards (IRBs)/Independent Ethics Committees (IECs), and Investigators.

Investigator safety reports must be prepared for suspected unexpected serious adverse reactions (SUSARs) according to local regulatory requirements and the Sponsor's policy and forwarded to the Investigators as necessary.

An Investigator who receives an Investigator safety report describing an SAE or other specific safety information (e.g., summary or listing of SAEs) from the Sponsor will review and then file it along with the Investigator's Brochure and will notify the IRB/IEC, if appropriate according to local requirements.

8.4.3 Pregnancy

An UPT will be performed at the time points designated in the SoA ([Table 1](#) and Table 13) for WOCBP. Women who are pregnant or breastfeeding may not be administered TMB-001 ointment.

If a pregnancy is reported, the Investigator should inform the Sponsor within 24 hours of learning of the pregnancy and should follow the procedures outlined in [Appendix 4](#).

Abnormal pregnancy outcomes (e.g., spontaneous abortion, fetal death, stillbirth, congenital anomalies, ectopic pregnancy) are considered SAEs.

8.5 Treatment of Overdose

Overdose in this study can be defined as either oral ingestion of a tube of TMB-001 or applying the TMB-001 ointment more often than the protocol specified regimen of twice daily.

Oral ingestion of an 80-gram tube of TMB-001 ointment 0.05% is calculated to result in less exposure than achieved with the recommended dosage of oral isotretinoin (80 mg/day). Consequently, the theoretical occurrence of symptoms of overdosage (e.g., hypervitaminosis A) is highly unlikely.

If a subject does receive an overdose of TMB-001 ointment, the subject should be counseled about the teratogenicity of isotretinoin and counseled on the prevention of pregnancy. Any WOCBP must be evaluated for pregnancy and must be warned to avoid pregnancy per the contraceptive measures outlined in [Appendix 4](#) for at least 1 month after overdose. Men should use a condom or avoid reproductive sexual activity with a female who is or might become pregnant for at least 1 month after an overdose. Subjects who present with an overdose should not donate blood for at least 1 month.

In the event of an overdose, the Investigator should:

1. Contact the Medical Monitor immediately.
2. Closely monitor the subject for any AEs, SAEs, and laboratory abnormalities for 1 month after the overdose.
3. Obtain a plasma sample for PK analysis if requested by the Medical Monitor (determined on a case-by-case basis).
4. Document the quantity of the excess dose as well as the duration of the overdose in the eCRF.

Decisions regarding dose interruptions or modifications will be made by the Investigator in consultation with the Medical Monitor based on the clinical evaluation of the subject.

9 OPTIONAL MAXIMAL USE ARM

[figure not shown]
9.1 Study Design

The aim of the open-label Optional Maximal Use arm is to evaluate the systemic exposure and safety of topical TMB-001 0.05% ointment for the treatment of RXLI or ARCI under conditions of maximal use in adult and pediatric subjects.

This study arm will use a staggered entry ([Figure 2](#)):

1. Adult CI subjects (≥ 17 years; n=16) and pediatric CI subjects (aged 12-16 years; n=7-9) receive TMB-001 0.05% BID for 14 days.
2. Interim analysis of PK parameters for subjects aged 12 years to adult are obtained over the 15-day period.
3. Based on the exposure data of subjects aged 12 years to adult, pediatric subjects (aged 6-11 years; n=7-9) will be enrolled and receive TMB-001 0.05% BID for 14 days.
4. Following the completion of the 14-day PK period, subjects will receive an additional 10 weeks of open-label TMB-001 0.05% BID.

Figure 2 Optional Maximal Use Arm Schema

Abbreviations: ARCI = Autosomal Recessive Congenital Ichthyosis; BID = Twice Daily; BSA = Body Surface Area; CI = Congenital Ichthyosis; PK = Pharmacokinetic; RXLI = Recessive X-linked Ichthyosis

Subjects at the end of the study or subjects discontinued from the study at any time will be followed-up for additional 2 weeks for AEs.

9.1.1 Discussion of Study Design

Subjects will be enrolled according to study eligibility criteria ([Sections 5.1 and 5.2](#)). The study treatment duration for PK sampling is 14 days which is expected to be sufficient for drug accumulation to occur. Subjects will then be provided open-label TMB-001 0.05% ointment BID up to Week 12. One additional PK sample will be acquired at completion of the study to check for maintenance of steady state pharmacokinetics.

The Optional Maximal Use arm will enroll subjects with CI (instead of healthy volunteers) as there are physiological differences between diseased and healthy skin. However, the PK data from this study will be compared with oral isotretinoin (single dose of 80 mg) exposure data in healthy subjects from other studies.

Application of the TMB-001 0.05% ointment to 75%-90% of the BSA allows for a large amount of study treatment to be applied and is more in line with how TMB-001 0.05% ointment may be used in clinical practice.

The study is designed to mitigate safety risks for pediatric subjects by conducting an interim PK analysis after treatment of subjects aged 12 years to adult with BID TMB-001 0.05% ointment for 14 days. Subsequent enrollment of pediatric subjects (aged 6-11 years) will be based on exposure data of subjects aged 12 years to adult.

9.1.2 End of Study Definition

A subject is considered to have completed the study if he/she has completed the last scheduled visit (Visit 8, Table 13). The end of the study is defined as the date of the last visit of the last subject in this study.

Table 13 Schedule of Assessments Optional Maximal Use Arm

	Screening	Baseline ^b						EOS/ET	Safety follow-up
Visit^a	1	2	3^c Remote possible	4 Remote possible	5^c Remote possible	6^c Remote	7 Remote	8	9^d (Optional remote)
Day	-90 to -7	1	12	14	15	28 (±7 days)	56 (±7 days)	84 (±7 days)	98 (±2 days)
Informed consent/assent	X								
Genetic testing/confirmation	X								
Inclusion/exclusion criteria including confirmation of % BSA	X	X ^e							
Medical history & demographics	X	X (updated)							
Physical examination ^f	X	X ^g						X	
Demonstrate how to apply the study treatment		X							
Clinical laboratory testing ^h	X							X	
Concomitant medication	X	X			X	X	X	X	
Vital signs ⁱ	X	X							X
Serum hCG pregnancy test for WOCBP ^j	X								
Urine pregnancy test ^k for WOCBP ^j		X				X	X	X	
IGA-scaling and fissuring assessment		X							X
Itch-Numeric Rating Scale		X	X	X	X	X	X	X	
Age-appropriate Dermatology Life Quality Index ^l		X							X
Ichthyosis Quality of Life-32 ^m		X	X	X	X	X	X	X	
Local skin reactions ⁿ		X	X	X	X	X	X	X	

	Screening	Baseline ^b						EOS/ET	Safety follow-up
Visit^a	1	2	3^c Remote possible	4 Remote possible	5^c Remote possible	6^c Remote	7 Remote	8	9^d (Optional remote)
Day	-90 to -7	1	12	14	15	28 (±7 days)	56 (±7 days)	84 (±7 days)	98 (±2 days)
Subject eDiary: Train (T), Dispense (D), Review (R),		T+D	R	R	R	R	R	R	
Study treatment accountability and dispensation to subject ^e		X		X	X			X	
Pharmacokinetic assessments		X ^p	X ^q	X ^r	X ^s			X ^t	
Adverse events		X	X ^u	X	X	X	X	X ^v	X

Abbreviations: EOS = End of Study; hCG = Human Chorionic Gonadotropin; IGA = Investigator's Global Assessment

- a. Visits at Screening and Baseline and EOS must be performed at the investigational site. Visits at Day 12, 14 and 15 can be performed remotely. Visits at Day 28 and Day 56 are scheduled remote visits.
- b. Screening assessments (except for genetic testing) may be performed up to 90 days prior to Visit 2 (Baseline) for those qualified subjects who are eligible to enroll in the study but require washout of medications prior to enrolling into the Treatment Phase of the study. Genetic confirmation should be obtained prior to conducting additional eligibility assessments in the screening period. There is no window for obtaining genetic confirmation, it can be obtained at any time following consent and with no restriction until Visit 2 (Baseline).
- c. Visits 3, 5 and 6 will be performed only in subjects ≥12 years.
- d. Subjects at the end of the study or subjects discontinued from the study at any time will be followed-up for additional 2 weeks for AEs.
- e. For subjects who require genetic testing, or a washout period related to exclusionary medications, reaffirm these subjects meet all protocol requirements at Visit 2 (Baseline).
- f. Examination will include head and neck, dermatologic, cardiovascular, respiratory, gastrointestinal (abdomen), and gross motor and gait assessments. Additional examinations will be conducted at Visit 2 (Baseline) to identify any changes since the Screening, at Visit 8 (EOS) to assess changes throughout the study. Abnormalities at Visit 1 (Screening) and Visit 2 (Baseline) will be recorded as medical history. Any new or worsening abnormality at all subsequent visits will be recorded as AEs.
- g. If there are less than two weeks between Visit 1 (Screening) and Visit 2 (Baseline), the physical examination at the Visit 2 (Baseline) includes only a dermatological assessment.
- h. Clinical laboratory tests (hematology, clinical chemistry, routine urinalysis) are provided in Table 17. Subjects must be fasting (at least 8 hours) for Visit 1 (Screening) and, if possible, at Visit 8 (EOS). However, if a subject arrives at the clinic for Visit 8 (EOS) without fasting for at least 8 hours, laboratory specimens may be collected as non-fasting, at the discretion of the Investigator and documented as such on the laboratory requisition form.
- i. Assessments will be made after the subject has rested in a seated position for at least 5 minutes. Height and weight will also be measured at Visit 1 (Screening).

- j. The term WOCBP is defined in [Appendix 4](#).
- k. All urine pregnancy tests must have a minimum sensitivity of 25 mIU β -hCG/mL.
- l. Subjects ≥ 16 years will be assessed using the Dermatology Life Quality Index (DLQL) while subjects < 16 years will be assessed using the Children's Dermatology Life Quality Index (CDLQI).
- m. Ichthyosis Quality of Life-32 (IQoL-32) will be used for subjects > 15 years.
- n. For visits performed remotely, local skin reactions will be assessed via the Subject eDiary.
- o. Instruction for study treatment administration will be provided in paper form and will be included in the Subject eDiary.
- p. Pre-dose sample (within 1 hour before dosing) and extensive post-dose sampling (1, 2, 4, 6 and 12 hours post-dose and within 1 hour before second dose)
- q. Single morning sample (pre-dose within 1 hour before morning dose)
- r. Pre-dose sample (within 1 hour before morning dose) and extensive post-dose sampling (1, 2, 4, 6 and 12 hours post-dose)
- s. Single morning sample (~24 hours after dose on Day 14)
- t. Single sample (within ± 7 days of Day 84)
- u. During any washout and screening periods, any changes in the health of subjects should be recorded as changes in medical history unless an event occurred as a result of a study-related procedure and was unanticipated. In such cases, the event should be recorded as an AE and reported to the Institutional Review Board/Independent Ethics Committee as an “unanticipated problem” in accordance with local procedure.
- v. Any treatment-related AEs that are ongoing at Visit 8 (EOS) must be followed until resolution or stabilization.

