1.2 Schedule of Assessments (SoA)

Table 1 Schedule of Assessments

	Screening	Baseline ^b							EOS/ ET	Safety follow- up
Visit ^a	1 (could be split in 2)	2	3 (remote)	4	5	6 ^c	7	8 (remote)	9	10 ^d (remote)
	-90 to -7 Days	Day 0	Day 14 (± 1 day)	Day 28 (±4 days)	Day 56 (±7 days)	Day 84 (±7 days)	Day 112 (±7 days)	Day 140 (±7 days)	Day 168 (±7 days)	Day 182 (±2 days)
Informed consent/assent	X									
Genetic testing/confirmation	X									
Inclusion/exclusion criteria	X	X ^e								
Medical history & demographics	X	X (updated)								
Physical examination ^f	X	X ^g				X			X	
Randomization		X ^h				X ⁱ				
Demonstrate how to apply the study treatment		X								
Clinical laboratory testing ^j	X					X			X	
Concomitant medication	X	X	X	X	X	X	X	X	X	
Vital signs ^k	X	X		X	X	X	X			X
Serum hCG pregnancy test for WOCBP ^l	X									
Urine pregnancy test ^m for WOCBP ^l		X		X	X	X	X	X	X	
IGA-scaling and fissuring assessment ⁿ	X	X		X	X	X	X			X
VIIS-scaling assessment	X	X		X	X	X	X			X
Record percent of BSA in Treatment Area	X	X				X			X	

	Screening	Baseline ^b							EOS/ ET	Safety follow- up
Visit^a	1 (could be split in 2)	2	3 (remote)	4	5	6^c	7	8 (remote)	9	10^d (remote)
	-90 to -7 Days	Day 0	Day 14 (± 1 day)	Day 28 (± 4 days)	Day 56 (± 7 days)	Day 84 (± 7 days)	Day 112 (± 7 days)	Day 140 (± 7 days)	Day 168 (± 7 days)	Day 182 (± 2 days)
Itch-Numeric Rating scale ^v		X	X	X	X	X			X	
Age-appropriate Dermatology Life Quality Index ^o		X				X			X	
Ichthyosis Quality of Life- 32 ^p		X				X			X	
Photography ^q		X		X	X	X			X	
Local skin reactions ^r		X	X	X	X	X	X	X	X	
Subject eDiary: Train (T), Dispense (D), Review (R)		T+D	R	R	R	R	R	R	R	
Study treatment accountability and dispensation to subject ^s		X		X	X	X	X		X	
Adverse events		X	X ^t	X	X	X	X	X	X ^u	X

Abbreviations: BSA = Body Surface Area; CI = Congenital Ichthyosis; EOS = End of Study; ET = Early Termination; hCG = Human Chorionic Gonadotropin; IGA = Investigator's Global Assessment; VIIS = Visual Index for Ichthyosis Severity; WOCBP = Women of Childbearing Potential

- Visits at Screening, Baseline, V6 and V9 must be performed at the investigational site. Visits 4, 5, and 7 should be performed at the investigational site but can also be performed as telemedicine visits. Visits 3, 8 and 10 are scheduled remote visits.

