2.3.1 Risk/ burden in minors

The expected risk/burden in minors is expected to be similar to subjects over the age of 18 years. The current study proposes similar amounts of investigational product applied/m², regardless of age. The safety profile achieved in minor subjects in the Phase 2A and Phase 2B programs was similar to that of older subjects. Local toxicity and skin reactions will be consistently evaluated throughout the trial in these minor subjects. Risk to children in this program should be compared with lack of on-label alternative products for treatment of congenital ichthyosis in children and adolescents; for example, acitretin is not approved for use in children with congenital ichthyosis in the European Union.

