6.5 Concomitant Therapy

Prohibited medication and treatments including the washout periods are summarized in Table 7.

- Non-petrolatum bland emollients^a and OTC low potency hydrocortisone (e.g., 1% cream) may only be used in the event of severe discomfort (e.g., burning/erythema/itch) (after Week 3 in the Phase III study and during the entire time in the Optional Maximal Use arm) and if it is the opinion of the Investigator that a drug interruption (per [Section 7.1](#))

^a Subjects enrolled in the study will use mandatory bland emollients during the Induction Period (1-3 weeks). After the Induction Period, bland emollients will be prohibited for these subjects until the EOS visit. Subjects enrolled into the Optional Maximal Use arm should discontinue the use of bland emollients at Visit 2 (Baseline).

alone will not relieve the symptoms and these may cause the subject to discontinue from study. The duration of the mitigation plan should not exceed 2 weeks.

- Topical antibiotic or antifungal treatments can be used after consultation and at the discretion of the Investigator. Systemic antifungals or antibiotics must be prescribed by the Investigator if necessary to avoid risk of more serious or broader infections.
- Subjects should limit exposure to UV via sunlight and avoid tanning beds.

Table 7 Prohibited Medication and Treatments Including Time Point of Discontinuation

Prohibited Medication	Time Point of Discontinuation

 • Topical retinoids • Topical prescription or over-the-counter therapies 	2 weeks before Visit 2 (Baseline)

 • Keratolytics • Topical corticosteroids 	5 days before Visit 2 (Baseline)

 • Bland emollients 	
 • Visit 2 (Baseline) – for Optional Maximal Use arm • Visit 4 (Week 4) – for Phase III study
• Over-the-counter low potency hydrocortisone	Visit 2 (Baseline)
Prohibited Systemic Treatment	Time Point of Discontinuation

 • Systemic retinoids 
 ◦ Isotretinoin ◦ Acitretin 	
 • 12 weeks before Visit 2 (Baseline) – for Optional Maximal Use arm • 1 year before Visit 2 (Baseline) – for Phase III study • 3 months before Visit 2 (Baseline)

 • Vitamin A supplements • St. John's Wort • Other therapies intended for CI or may improve CI 	4 weeks before Visit 2 (Baseline)

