9.2 Study Treatment

Treatments administered to subjects in the Optional Maximal Use arm, including frequencies, dosing and durations are the following:

- Study treatment will be applied to 75% to 90% of the BSA
- Subjects will be dosed for 14 days BID with TMB-001 0.05% for PK measurements. During these 14 days, any interruption of dosing, or any missed dose will result in excluding the subject from the PK sampling. It is imperative that continuous BID dosing occur days 1-14.
- Subjects will subsequently be dosed BID for an additional 70 days (10 weeks with open-label TMB-001 0.05% ointment)

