9.3.2 Pharmacokinetic Assessments

Blood sampling and PK analyses for subjects aged 12 years to adult will be performed at the time points designated in the SoA (Table 13) and as indicated in Table 14. PK analyses include serum levels of isotretinoin, tretinoin, 4-oxo-isotretinoin and 4-oxo-tretinoin. Blood sample collection instructions are provided in the Laboratory Manual.

Blood sampling and PK analyses for subjects aged 6 to 11 years will be performed at the time points designated in the SoA (Table 13). For these subjects, the number of blood draws will not exceed 2 time points per visit on Days 1 and 14 (total 4 blood draws, Table 15) and blood volume for PK sampling will not exceed 16 ml of blood in total (4 ml per time point). The Investigators will adhere to the site-specific blood volume limits for PK analyses to ensure minimal distress to the pediatric patients aged 6 to 11 years. Accordingly, if PK profile cannot be obtained for a given visit due to logistical challenges, the Investigator should aim to at least obtain sample for trough PK (pre-dose).

Table 14 Blood Sampling Schedule for Subjects 12 years to adult

Study Visit/Day	Sampling
Visit 2/Day 1	
• Pre-dose sample, (within 1 hour before dosing)

	
 Extensive post-dose sampling (1, 2, 4, 6 and 12 hours post -dose and within 1 hour before second dose)
Visit 3/Day 12	Single morning sample (pre-dose within 1 hour before morning dose)
Visit 4/Day 14	
 Pre-dose sample (within 1 hour before morning dose), Extensive post-dose sampling (1, 2, 4, 6 and 12 hours post-dose)
Visit 5/Day 15	Single morning sample (~24 hours after dose on Day 14)
Visit 8/Day 84	Single sample within \pm 7 days of Day 84

Table 15 Blood Sampling Schedule for Subjects 6 to 11 years

Study Visit/Day	Sampling
Visit 2/ Day 1	Pre-dose (within one hour of dosing), single post-dose at time point to be determined
Visit 4/Day 14	Pre-dose (within one hour of dosing), single post-dose at time point to be determined

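### Maximal-use children aged 6-11 have no scheduled safety check between Day 14 and Day 56, because the remote, blood-free Day 28 visit is limited to subjects aged 12 and over

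*Protocol*

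**What the plan says.** Table 13 schedules the maximal-use arm at Day 1 (Visit 2), Days 12, 14 and 15 (Visits 3 to 5), Day 28 ±7 (Visit 6), Day 56 ±7 (Visit 7) and Day 84 ±7 (Visit 8), with a safety follow-up at Day 98. AEs, LSRs and the eDiary are marked at every one of Visits 2 to 8. Footnote c then removes three visits for the youngest group: "Visits 3, 5 and 6 will be performed only in subjects ≥12 years".

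Footnote a adds: "Visits at Day 28 and Day 56 are scheduled remote visits". Footnote n gives the method at such visits: "For visits performed remotely, local skin reactions will be assessed via the Subject eDiary".

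Section 9.3.2 limits sampling in ages 6-11: "the number of blood draws will not exceed 2 time points per visit on Days 1 and 14".

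Dosing continues through the interval in question. Section 9.2 has subjects apply the ointment BID to 75-90% of body surface for 14 days, and then: "Subjects will subsequently be dosed BID for an additional 70 days". Section 6.5, footnote a, adds: "Subjects enrolled into the Optional Maximal Use arm should discontinue the use of bland emollients at Visit 2 (Baseline".

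The main-study schedule (Section 1.2, Table 1) places Visit 4 at Day 28 ±4 with AEs, LSRs and eDiary review, and has no age restriction. Its footnote a allows some flexibility in mode: "Visits 4, 5, and 7 should be performed at the investigational site but can also be performed as telemedicine visits".

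Section 2.3.1 says of children: "Local toxicity and skin reactions will be consistently evaluated throughout the trial in these minor subjects".

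**The concern.** The only reason the protocol offers for a lighter schedule at ages 6-11 is to limit blood draws. That fits Visits 3 and 5, and little monitoring is lost with them, since Visit 4 on Day 14 falls within one or two days of both. It does not fit Visit 6, and no other reason is given.

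What goes with Visit 6 is the Week 4 review. Section 2.2 reports that most Phase IIb skin reactions, under BID dosing, occurred at Weeks 2 and 4. Maximal-use children start BID on Day 1 over at least 75% of body surface with bland emollient stopped. Main-study children of the same age start QD with mandatory emollient for three weeks, yet they have a Day 28 check.

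The Section 7.1 interruption steps run from 3 to 14 days, and Section 6.5 caps rescue emollient or hydrocortisone at 2 weeks. A whole reaction, interruption and rescue could begin and end between two scheduled reviews. Local safety and tolerability in adult and pediatric subjects is this arm's stated safety objective (Table 3).

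**Working it through.** **1. Does Visit 6 involve blood?** Tables 14 and 15 (Section 9.3.2) list no Day 28 sample. The maximal-use blood-volume table in Appendix 2 has columns for Visits 1, 2, 3, 4, 5 and 8 only. Summing those columns should give the stated totals if nothing is drawn at Visits 6 or 7:

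- Ages 6-11, North America: 3.5 + 8 + 0 + 8 + 0 + 3.5 = 23 mL (stated 23)
- Ages 6-11, Europe: 6 + 8 + 0 + 8 + 0 + 6 = 28 mL (stated 28)
- Ages 12-17: 71 and 76 mL; ages 18+: 81 and 88 mL (all as stated)

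Visit 6 therefore has no blood draw in any age group. The items marked there are concomitant medication, urine pregnancy test where applicable, I-NRS, IQoL-32 (over 15 years only), LSRs, eDiary review and AEs.

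**2. Scheduled AE/LSR contacts through Day 84.** Gap = day of later visit minus day of earlier visit; windows applied at each end where they exist.

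| Group | Contact days after baseline | Number | Longest nominal gap | Longest gap with windows |
|---|---|---|---|---|
| Maximal use, 6-11 | 14, 56, 84 | 3 | 56 − 14 = 42 | 63 − 14 = 49 |
| Maximal use, ≥12 | 12, 14, 15, 28, 56, 84 | 6 | 56 − 28 = 28 | 63 − 21 = 42 |
| Main study, any age | 14, 28, 56, 84 | 4 | 56 − 28 = 28 | 91 − 49 = 42 |

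The shortest permitted Day 14 to Day 56 gap for ages 6-11 is 49 − 14 = 35 days.

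**3. Nominal applications in the first 28 days.** Maximal use: 28 × 2 = 56. Main study: 21 × 1 + 7 × 2 = 35.

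**4. Other items lost with Visit 6.**

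- Concomitant medication is not marked at Visit 4, so ages 6-11 have no scheduled check of it between Day 1 and Day 56.
- For any post-menarchal girl, the first interval between pregnancy tests is 56 − 1 = 55 days (49 − 1 = 48 to 63 − 1 = 62). For subjects ≥12 who are tested it is 28 − 1 = 27 days (21 − 1 = 20 to 35 − 1 = 34).

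**5. If Visit 6 is kept.** The 42-day gap splits into 28 − 14 = 14 days (7-21) and 56 − 28 = 28 days (14-42), which nominally matches the main study.

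**The case against.** The strongest reply accepts the reading of footnote c and disputes its weight.

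- **Contact counts.** Days 12, 14 and 15 are close to a single contact, so the meaningful comparison within the arm is 3 against 4. That is right: the loss is one remote contact.
- **Windows.** At the extremes of the windows, the maximum is 49 days against 42 elsewhere, a difference of 7. This is also correct. The nominal contrast of 42 against 28 remains, and the other groups reach 42 only when two visits sit at opposite ends of their windows.
- **Other routes for reporting.** Subjects keep the eDiary, can report events unprompted, fall under the Section 7.1 interruption rules, and may use bland emollient or low-potency hydrocortisone for severe discomfort throughout this arm (Section 6.5). All of this stands. The documents do not say how often LSR entries are made, so how far Visit 7 would rest on memory is unknown. None of these routes is a scheduled review: Table 13 next marks one for these children at Day 56.
- **Exposure.** Subjects ≥12 in this arm have the same regimen, and Table 4 gives similar daily amounts per m² (0.019 g for a 6-year-old, 0.020 g for an adult). That answers any claim of heavier dosing by age. It gives no reason for checking the younger group less often on the same regimen.
- **Phase IIb timing.** Section 2.2 calls most reactions mild or moderate and does not split Weeks 2 and 4, so the share at Week 4 is unknown. Week 2 is retained as Visit 4.
- **Reach.** The pregnancy-test subgroup may be empty, this arm's data are planned as listings, and the documents do not show whether the cohort is still enrolling. These points limit the consequences but do not explain the footnote.

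**Conclusion.** The concern holds. Footnote c leaves all 7-9 planned children aged 6-11 without a scheduled AE, LSR or eDiary check for 42 days nominally (35-49 with the window), against a longest nominal gap of 28 days for older subjects in the arm and for main-study children. Limiting blood draws cannot account for it.

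The consequence is possible late detection and poorer capture of reactions around Week 4; under-reporting is not shown. Section 2.3.1 sets no interval, so the schedule is in tension with its statement on children but does not contradict it. The interim pharmacokinetic step in Section 9.1.1 governs entry to the cohort and is untouched, as are the primary, key secondary and pharmacokinetic objectives.

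The conclusion assumes that Table 13 and its footnotes are the full schedule of contacts; nothing elsewhere in the documents adds one. The change should be made because it is cheap and serves the safety of the youngest children in the trial.

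**What to change.** Amend footnote c of Table 13 so that only Visits 3 and 5 are restricted to subjects aged 12 and over. The remote Visit 6 at Day 28 ±7 then applies at every age and restores the AE check, the eDiary-based LSR assessment, the concomitant medication check and, where applicable, the urine pregnancy test. It does not add an in-person skin examination.

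The cost is one footnote edit, which can go into the next amendment, and one extra remote contact for each of 7-9 children, with no blood draw and no site visit. If the cohort has already completed, state the longer interval when its safety listings are reported.
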